2.7.1.1 Adverse events of special interest / grouping of AEs

Analyses focused on skin rash may be provided. Further details will be included in the TFL shells document.

2.7.2 Deaths

All deaths (if any) will be listed using the Safety set.

2.7.3 Laboratory data

Laboratory data collected sparsely (eg. for reflex testing for urine microscopy or safety follow-up testing for renal/hepatic events) will be listed but not included in summaries.

Biomarkers not included as part of trial safety monitoring (Table 8-1 of the study protocol) included among the laboratory data will be analyzed as described in [Section 2.11](#). Specifically the following parameters will be considered as exploratory outcome biomarkers:

Table 2-2 Laboratory parameters to be managed as biomarkers

Code (LBPARM)	Description (parameter)	Code (LBTEST)
TRIG	Triglycerides	TRIG
VLDL	VLDL cholesterol	VLDL
LDLDIRCT	LDL Cholesterol (Direct)	LDL
NHDL	Non HDL cholesterol	NONHDL
HDL	HDL cholesterol	HDL
HSCRP	High sensitivity C-reactive protein	CRP
LDLCALM	LDL Cholesterol (Calculated)	LDL
CHOL	Cholesterol	CHOL
APOA1	Apolipoprotein A1	APOA1
APOB	Apolipoprotein B	APOB
Not available yet	vWF	not available yet
Not available yet	Lp(a)	not available yet

Only Low Density Lipoprotein Cholesterol (LDL-C) will be reported as both safety laboratory data and an exploratory outcome biomarker. Data collected on local labs won't be reported. In the summaries, laboratory results expressed as $<x$ or $>y$ will be considered as $\frac{1}{2}x$ or y , respectively.

Other derivations related to laboratory parameters are described in [Section 5.3](#)

The following descriptive summaries will be produced for laboratory data for each laboratory parameter

- Actual value and change from baseline summaries by treatment and timepoint as well as by treatment sequence
- Shift tables using the low/normal/high/(low and high) classification to compare baseline to the worst on-treatment value will be presented for all the parameters with normal ranges available only by treatment sequence.

Estimated glomerular filtration rate (eGFR) data (mL/min/1.73 m²) as calculated by the CKD-EPI equation will be categorized according to these rules:

G1 (Normal) = ≥ 90

G2 (Mildly decreased) = 60-89

G3a (Mildly to moderately decreased) = 45-59

G3b (Moderately to severely decreased) = 30-44

G4 (Severely decreased) = 15-29

G5 (Kidney failure) = < 15

Shift table for this parameter will be based on the categories described above.

For categorical parameters, the frequency and percentage of participants falling in each category will be presented in the summary tables.

In the analyses by treatment and timepoint, the time will be referred to the start of each dosing period. Therefore for instance a day 43 assessment will be considered a 3-week assessment and assigned to the treatment received by the participant in the second dosing period (except in treatment sequence 1). Time will be managed differently for the participants randomized to treatment sequences 1 and 5. In this case time will be referred to the start of the first treatment (MAS825 in treatment sequence 1, Placebo for treatment sequence 5). Therefore for these participants assessments after 6, 9 and 12 weeks will also be derived.

Analyses by treatment won't be performed for the laboratory data collected just at the start and at the end of the trial (Coagulation panel and Urinalysis).

In the analyses by treatment sequence and timepoints the following time points will be reported:: screening, baseline, Days 22, 43, 64, 85 and 92.

Box-plots by treatment sequence and time, as well as by treatment will be provided. In the latter case the horizontal axis will include the baseline and the 3-week assessments. Weeks 6,9,12 distributions will be plotted just for the placebo and the MAS arm. Further details will be included in the TFL shells document.

Listing for participants with lab values outside the normal range (per normal ranges provided in the source dataset) will be provided. If there is any abnormal lab value for a participant, all measurements of this lab value for the participant will be presented in this listing with the abnormal values flagged.

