9.4.1 Safety endpoints

For all safety analyses, the safety set will be used. All listings and tables will be presented by treatment sequence.

Adverse events

The number (and percentage) of participants with treatment emergent AEs will be summarized by overall count, by treatment/dose, primary system organ class, and preferred term. An additional summary by treatment sequence primary system organ class, preferred term, and maximum severity will be reported.

Treatment-emergent AEs are those with an onset after the start of a specific dosing period, or which were present prior to the start of the dosing period but increased in severity, changed from being not suspected to being suspected of study treatment relationship, or developed into SAEs after the start of the dosing period.

For the purposes of these summaries, a dosing period is defined as an approximate 3-week interval between scheduled visits as given in the study design figure ([Figure 1-1](#)). For example, the first dosing period will begin at Day 1 (randomization) and end on the Day 22 visit, at which point the next treatment will be administered according to the specific treatment sequence.

A participant with multiple AEs within a primary system organ class is only counted once towards the total of the primary system organ class.

All information obtained on AEs will be displayed by treatment sequence and participant.

A participant with multiple AEs within a primary system organ class is only counted once towards the total of the primary system organ class.

AEs which will be counted for a specific treatment period are those which are treatment-emergent. These events are those with an onset after the start of the treatment period, or which were present prior to the start of the treatment period but increased in severity, changed from being not suspected to being suspected of study treatment relationship, or developed into SAEs after the start of the treatment period.

Vital signs

All vital signs data will be summarized by overall count (%) and by treatment/dose and visit/time.

12-lead ECG

All ECG data will be summarized by overall count (%) and by treatment/dose and visit/time.

Clinical laboratory evaluations

All laboratory data will be summarized by overall count (%) and by treatment/dose, and visit/time. An additional summary by treatment sequence, will be reported.

Immunogenicity

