2.1 Data analysis general information

The final CSR analysis will be performed by Novartis. SAS version 9.4 or later software will be used to perform all data analyses and to generate tables, figures and listings.

General analysis conventions

Unless otherwise specified: categorical data will be presented as frequencies and percentages; continuous data will be presented as n, mean, standard deviation (SD), median, minimum, and maximum.

For PK concentration and PK parameters, coefficient of variation (CV) (%), geometric mean, and geometric CV% will be presented in addition to the previously mentioned summary statistics.

CV% is calculated as follows:

$$100 * (\text{SD} / \text{arithmetic mean}).$$

Geometric CV (%) is calculated as follows:

$$\text{sqrt}(\exp(\text{variance for log transformed data}) - 1) * 100.$$

Unscheduled assessments

The following points summarize the rules for unscheduled assessments:

- Baseline: All unscheduled assessments before the first dose may be included for consideration when calculating the baseline value.
- In summary tables by visit, unscheduled assessments should not be included unless they qualify as baseline.
- In shift tables and table of abnormal values all unscheduled assessments are included.

Unscheduled assessments will be reported with the scheduled assessments in the listings.

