2.1.1.2 Treatment sequence

In this study, participants are randomized to either of the five treatment sequences, each contains 4 dosing periods. The study treatment planned for each dosing period within each treatment sequence is shown below:

Treatment sequence 1: MAS825 – Placebo – Placebo – Placebo. Note that the effect of MAS825 is expected to persist over the entire 12-week treatment period. Therefore data collected in this sequence, after week 3 will be still assigned to MAS825.

Treatment sequence 2: Placebo – DFV890 10 mg – DFV890 25 mg – DFV890 100 mg

Treatment sequence 3: Placebo – DFV890 25 mg – DFV890 50 mg – DFV890 100 mg

Treatment sequence 4: DFV890 10 mg – DFV890 25 mg – DFV890 50 mg – DFV890 100 mg

Treatment sequence 5: Placebo – Placebo – Placebo – Placebo

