2.1.1.10 On-treatment period (safety analyses)

On-treatment period starts at day 1 and ends after 30 days from the last dosing.

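### Laboratory shift tables are planned only by treatment sequence, so shifts cannot be counted by DFV890 dose or against the pooled placebo sessions

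*SAP*

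**What the plan says.** SAP 2.7.3 plans shift tables to "compare baseline to the worst on-treatment value will be presented for all the parameters with normal ranges available only by treatment sequence". Three other SAP rules determine which values can be the worst one:

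- SAP 2.1.1.10 sets the safety window: "On-treatment period starts at day 1 and ends after 30 days from the last dosing". The Day 92 end-of-study visit falls inside it.
- SAP 2.1, on unscheduled assessments: "In shift tables and table of abnormal values all unscheduled assessments are included". By-visit summaries leave those values out unless they serve as baseline.
- SAP 2.1.1.2 defines the sequences. Two of the three DFV890 sequences begin on placebo: "Treatment sequence 2: Placebo – DFV890 10 mg – DFV890 25 mg – DFV890 100 mg" and "Treatment sequence 3: Placebo – DFV890 25 mg – DFV890 50 mg – DFV890 100 mg". The third does not: "Treatment sequence 4: DFV890 10 mg – DFV890 25 mg – DFV890 50 mg – DFV890 100 mg". Only one is placebo throughout: "Treatment sequence 5: Placebo – Placebo – Placebo – Placebo".

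SAP 2.7.3 also plans actual values and changes from baseline by treatment and by sequence, box-plots both ways, and a listing with abnormal values flagged. Coagulation and urinalysis are exempt from by-treatment analysis.

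Protocol 9.4.1 points two ways. Its opening rule puts every safety listing and table by treatment sequence. Its laboratory paragraph then says: "All laboratory data will be summarized by overall count (%) and by treatment/dose, and visit/time", with a summary by sequence as an addition. SAP section 4 names no specific change from the protocol.

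**The concern.** A shift table counts participants who move from a normal baseline to an abnormal value. Laid out by sequence, it mixes placebo, several DFV890 doses and the off-drug follow-up into one worst value per participant. A reader cannot tell whether a shift under Sequence 2 or 3 arose on placebo, at a given dose, or after treatment ended.

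The placebo comparison is also lost. Protocol Table 4-1 explains that Sequences 2 and 3 supply within-participant placebo data, and that Sequences 4 and 5 were included mainly to keep the blind. A by-sequence shift table discards the first source and leaves only the 2 participants in Sequence 5.

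Laboratory safety is a secondary endpoint. Protocol 2.3.1.3 reports transient neutrophil and white-cell decreases with DFV890, and Protocol 2.3.2.2 calls for renal monitoring because of preclinical findings. For transient changes, knowing the dosing session matters most.

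**Working it through.** **1. Allocation (Protocol 9.9.1, SAP section 3).** 28 participants at 4:4:4:1:1 give 28 × 4/14 = 8 in each of Sequences 1 to 3 and 28 × 1/14 = 2 in each of Sequences 4 and 5. This reproduces the stated 8/8/8/2/2. DFV890 participants: 8 + 8 + 2 = 18, of whom 16 start on placebo.

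**2. Sessions (SAP 2.1.1.2).** Placebo: 8 + 8 + 2 × 4 = 24, matching the 24 in SAP 2.4.1, from 8 + 8 + 2 = 18 participants. DFV890: 10 mg 8 + 2 = 10; 25 mg 8 + 8 + 2 = 18; 50 mg 8 + 2 = 10; 100 mg 8 + 8 + 2 = 18; total 56.

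**3. Values that can set the worst.** Hematology and chemistry are scheduled on Days 22, 43, 64, 85 and 92 (Protocol Table 1-2), giving 18 × 5 = 90 values in Sequences 2 to 4.

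- Day 22, Sequences 2 and 3: 16 values on placebo (pre-dose, and part of dosing period 1 under SAP 2.1.1.3).
- Day 92, Sequences 2 to 4: 18 values off drug. The last dose is on Day 84. At a half-life of about 10 hours (Protocol 4.3), 8 × 24/10 is about 19 half-lives.
- On DFV890: 90 − 16 − 18 = 56.

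Not on DFV890: 34/90 = 38%. Per participant this is 2 of 5 in Sequences 2 and 3, and 1 of 5 in Sequence 4.

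**4. Dilution, as an illustration.** The documents give no abnormality rates. Assume an independent per-visit risk p, doubled on DFV890, and compare cumulative risks over the same number of visits. At p = 5%:

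- Placebo, five visits: 1 − 0.95^5 = 22.6%.
- Sequences 2 and 3 as planned (two visits off DFV890, three on): 1 − 0.95² × 0.90³ = 34.2%; ratio 1.51.
- All five visits on drug: 1 − 0.90^5 = 41.0%; ratio 1.81.
- The three on-drug visits alone: (1 − 0.90³)/(1 − 0.95³) = 27.1%/14.3%; ratio 1.90.

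Range over p, same formulas:

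| p | Mixed, five visits | All five on drug | Three on-drug visits |
|---|---|---|---|
| 2% | 15.0/9.6 = 1.56 | 18.5/9.6 = 1.92 | 11.5/5.9 = 1.96 |
| 5% | 1.51 | 1.81 | 1.90 |
| 10% | 58.5/41.0 = 1.43 | 67.2/41.0 = 1.64 | 48.8/27.1 = 1.80 |

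**5. Placebo precision.** With no events, the Clopper-Pearson 95% upper limit is 1 − 0.025^(1/n): n = 2 gives 84%, n = 18 participants gives 19%, and n = 24 gives 14%. The last would need independent sessions, which repeated sessions in one participant are not.

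**The case against.** The strongest reply is that the information is available elsewhere. With 28 participants, the flagged listing lets anyone trace a scheduled abnormal value to its dose. Laboratory abnormalities that cause symptoms, are clinically significant or need therapy are adverse events (Protocol 8.6.1), and SAP 2.7.1 counts those by treatment with dosing sessions as denominator. By-treatment summaries include minimum and maximum. Frequencies for categorical parameters may show eGFR grades by treatment, though the SAP does not say so. Extra visits cannot hide an on-drug abnormality; they only add background. All of this stands and limits the point. What remains is that a listing has no counts or denominators, the summaries describe distributions rather than shifts, and an unscheduled abnormal value is left out of the by-visit summaries.

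A reader might infer that the SAP silently breaks a protocol promise. The documents do not support that: a by-sequence table follows the opening rule of Protocol 9.4.1, and that section never mentions shift tables. The fault is the unreconciled pair of sentences.

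A reader might also take platelet and liver shifts as expected DFV890 signals. Protocol 2.3.1.3 draws its platelet evidence from canakinumab, under MAS825, and Protocol 2.3 does not list liver among the DFV890 risks. Nor is a human renal effect established: Protocol 2.3.2.2 reports no evidence of one in the two clinical studies cited.

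Finally, a by-dose table has its own weakness. Doses escalate without washout, so an abnormality that begins at a low dose and persists would be counted again at each higher dose. That is correct, and the fix has to handle it.

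**Conclusion.** The point holds as a reporting gap that should be closed. No planned output counts baseline-to-abnormal laboratory shifts by DFV890 dose or against the 24 placebo sessions, and 38% of the scheduled hematology and chemistry values that can set the worst value in Sequences 2 to 4 are not on DFV890. The placebo-period part concerns Sequences 2 and 3 only; the Day 92 part concerns all three. Coagulation and urinalysis have no scheduled Day 22 value, so for them the placebo period matters only through unscheduled samples.

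Two larger readings should be avoided. The first is that the layout cuts a doubled risk from 2.0 to 1.5. That sets a per-visit ratio beside a cumulative one; on a like basis at 5%, the fall is from 1.81 to 1.51 (or from 1.90, using on-drug visits only), under assumed rates and independence. The second is that 40% of worst values in Sequences 2 and 3 come from visits off DFV890. That needs exchangeable visits, which a drug effect contradicts: under the doubling assumption, expected abnormal values per participant are 2 × 0.05 = 0.10 off DFV890 and 3 × 0.10 = 0.30 on it, so 25%.

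Including Day 92 follows the SAP's own window and is not an error; it affects attribution only.

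**What to change.** For hematology and chemistry, including eGFR categories, add a shift table by treatment:

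- Compare the Day 1 baseline with the worst scheduled or unscheduled value in each dosing session, with dosing sessions as denominator, as SAP 2.7.1 does for adverse events. Give the number of participants beside the number of sessions.
- Show MAS825 over its 12-week session, with a note that this spans four scheduled visits against one in a 3-week session.
- Put Day 92 in a separate follow-up row.
- Mark shifts already present at the start of a session, so that a persisting abnormality is not read as new at each higher dose.

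Keep the by-sequence table, and leave coagulation and urinalysis by sequence only. Reconcile the two statements in Protocol 9.4.1, and state in the SAP how both are met.

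The cost is one more descriptive table shell and a short SAP addition, with no new data. The downside is that sessions within a participant are correlated, so session percentages should not be given intervals that assume independence.

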2.7.4 Other safety data

2.7.4.1 12-lead ECG

All ECG parameters (absolute values and changes from baseline) will be descriptively summarized by treatment sequence and time. All ECG data will be listed by treatment sequence and participant. Box-plots by treatment sequence and time will be provided.

In the listings values will be flagged according to the following rules:

QT, QTcF

- New value of > 450 and ≤ 480 ms
- New value of > 480 and ≤ 500 ms
- New value of > 500 ms
- Increase from baseline of > 30 ms to ≤ 60 ms
- Increase from baseline of > 60 ms

- HR
 - Decrease from baseline $>25\%$ and a value < 50 beats per minute
 - Increase from baseline $> 25\%$ and a value > 100 beats per minute

- PR
 - Increase from baseline $>25\%$ and to a value > 200 ms
 - New value of > 200 ms

- QRS
 - Increase from baseline $>25\%$ and to a value > 120 ms
 - New values of QRS > 120 ms

The definition of 'new value' is any case meeting the criteria during the on-treatment period not already present at baseline.

Baseline definition is provided in [Section 2.1.1.9](#)

2.7.4.2 Vital signs

All vital signs data (absolute values and changes from baseline) will be summarized by treatment/treatment sequence and time. Time will be managed as previously described for labs data. All vital signs data will be listed by treatment sequence and time. Box-plots by treatment sequence and time as well as by treatment will be provided.

A listing for complete vital signs data for all participants will be presented with the abnormalities flagged according to the following rules:

Notable criteria (High/Low):

- Systolic blood pressure [mmHg]: >140/<90 mmHg
- Diastolic blood pressure [mmHg]: >90/<50 mmHg
- Pulse rate [bpm]: >90/<40 bpm
- Weight [kg]: >110/<35 Kg
- Temperature [°C]: >37.5/<35.0°C.

2.8 Pharmacokinetic endpoints

Plasma Ctrough of DFV890 and its metabolite, IBW042, will be descriptively summarized by CYP2C9 genotype, dose, and time point, including the frequency of concentrations below the LLOQ and reported as zero. Serum MAS825 concentrations will be summarized similarly without a breakdown by CYP2C9 genotype and considering a wider time interval.

Plasma Ctrough/concentrations of DFV890 and its metabolite, IBW042, will be descriptively summarized by dose, and by CYP2C9 genotype and dose, including the frequency of concentrations below the LLOQ reported as zero. Serum MAS825 concentrations will be summarized by time point.

Time will be defined at the dosing period level except in MAS825 analysis.

Individual plots and mean plots by CYP2C9 (for DFV890 and IBW02) and dose will also be provided.

2.9 PD and PK/PD analyses

Correlation analyses between plasma Ctrough of DFV890 and selected biomarkers and between concentrations of MAS825 and selected biomarkers may be performed by a scatterplot together with a regression line respectively. Correlation statistics such as Pearson correlation coefficient and its p-value may be presented on the graph as well.

2.9.1 Immunogenicity

2.9.1.1 Sample ADA Status

Immunogenicity analysis will be restricted to the MAS825 arm.

Each anti-drug anti-body (ADA) sample is assessed in a three-tiered ADA testing approach. All ADA samples are analyzed in the initial screening assay (first tier). Samples testing negative in the screening assay are not subject to a confirmatory assay. Samples testing positive in the screening assay are then subjected to the confirmatory assay to demonstrate that ADA are specific for the therapeutic protein product (second tier). The titer of confirmatory positive samples will be subsequently determined in the titration assay (third tier).

Samples can test negative in either the screening or confirmatory assay but for statistical analysis purposes they are not differentiated. The following properties of each sample will be provided in the source data (i.e. the third party data output (e.g. WLIMS) processed by PreAdvance):

- Result of assay according to pre-specified confirmatory cut point: 'POSITIVE', 'NEGATIVE', or 'NOT REPORTABLE'
- Titer: numerical representation of the magnitude of ADA response

Sample ADA status will be listed in the safety set and summarized by treatment and time point in the MAS arm. Overall prevalence will also be summarized including/excluding the baseline assessment.

2.10 Patient-reported outcomes

Not applicable.

2.11 Biomarkers

All participants in the PD analysis set will be included in the biomarker analysis. The following exploratory biomarkers may be analyzed in this trial and reported in the CSR.

- Pharmacodynamic, inflammation-related biomarkers:
 - Inflammatory biomarkers: hsCRP
 - Soluble Biomarkers: soluble ASC, hsIFN- γ , and vWF
- Immunophenotyping: A whole blood monocyte / neutrophil panel will evaluate the total cell count and percentage of monocyte and neutrophil subsets in peripheral blood of patients.
- Target capture biomarkers for MAS825: total IL-1 β , total IL-18 and IL-18bp.
- CVD-related biomarkers
 - Lipid parameters: total cholesterol, HDL-C, triglycerides (TGs), LDL-C, Lp(a), apolipoproteins

For each of the biomarker endpoints, the actual value, the change from baseline, and the percent change from baseline will be listed by treatment sequence, participant, and visit/timepoint. Summary statistics will be provided by treatment/treatment sequence and visit/timepoint for the actual value, the change from baseline and percent change from baseline. The frequency (n, %) of values outside of the limits of quantification will be reported in each table.

The following inflammation-related exploratory biomarkers: hsCRP, soluble ASC, hsIFN γ , vWF, Interleukin-1b (IL-1b), IL-18, IL-18bp and monocyte/neutrophil panel (whole blood) and disease-related biomarkers (LDL, Lp(a), and apolipoproteins) will be analyzed using a linear mixed effects model of the same form as the traditional model previously specified for the primary endpoint. When appropriate, the analysis will be restricted to DFV890 or MAS825 sessions with the corresponding control sessions.

As for the analysis on primary endpoint log transformations will be applied. Immunophenotyping endpoints considering percentages vs total monocytes/neutrophils will be summarized and listed while they won't be analyzed using any statistical model.

Corresponding plots showing the predicted response at each treatment dose (or time for MAS825) with associated 80% CIs will also be produced, together with individual plots by treatment (by time for MAS825 arm).

Handling of LLOQ and ULOQ

Biomarker data are reported as concentration results, measured using a specific assay with a working range defined by the two limits: Lower limit of quantification (LLOQ) and Upper limit

of quantification (ULOQ). Values which fall below the LLOQ or above the ULOQ are reported as $< \text{LLOQ} * \text{dilution factor}$ (dilution factor: if sample diluted and concentration measured still below LLOQ) and $> \text{ULOQ} * \text{dilution factor}$, respectively.

To ensure that biomarkers only have numerical values, censored values will be imputed as follows:

- Values below the LLOQ are replaced by $\text{LLOQ}/2$.
- Values above the ULOQ are replaced by ULOQ.

Imputed values are used for summary statistics, inferential analyses and plots (with a special symbol). Values below LLOQ and values above ULOQ are shown as such in the listings.

If the proportion of imputed data is more than 20% for any treatment group at any time point, a footnote is added to the summary statistics table stating that the proportion of values outside the limits of quantification is more than 20% for some treatment groups at some time points and that in such cases summary statistics may be heavily biased.

If the proportion of imputed data for a given biomarker, across all treatment groups and time points, is more than 50%, no summary statistics are provided and the data are only listed.

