9.5.1 Biomarkers

The following inflammation-related exploratory biomarkers (hsCRP, soluble ASC, CXCL9, CXCL10, hsIFN- γ , IL-1 β , and neutrophil activation/frequency in whole blood) and disease-related biomarkers (LDL and Lp(a)) will be analyzed using a linear mixed effects model of the same form as the traditional model specified for the primary endpoints in [Section 9.3.2](#).

Biomarker values above the Upper Limit of Quantification (ULOQ) will be imputed as ULOQ and values below the LLOQ will be imputed as LLOQ/2 for these analyses.

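### SAP 2.11 reports out-of-range biomarker results with the dilution factor but imputes them without it, so a diluted sample still above range is entered below its own reported bound

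*SAP*

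**What the plan says.** The subsection on quantification limits in SAP 2.11 makes four statements in sequence.

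- LLOQ and ULOQ belong to the assay: results are "measured using a specific assay with a working range defined by the two limits". Dilution is not part of that definition.
- Out-of-range results carry a dilution factor: "Values which fall below the LLOQ or above the ULOQ are reported as" less than LLOQ × dilution factor or greater than ULOQ × dilution factor, respectively. The SAP explains the factor as "dilution factor: if sample diluted and concentration measured still below LLOQ". That explanation names only the low side, but the factor is attached to both limits.
- The imputation has no factor. Low side: "Values below the LLOQ are replaced by" LLOQ/2. High side: "Values above the ULOQ are replaced by ULOQ".
- The substituted numbers enter the results: "Imputed values are used for summary statistics, inferential analyses and plots (with a special symbol"). For the modelled biomarkers, "As for the analysis on primary endpoint log transformations will be applied".

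Protocol 9.5.1 has the same rule and does not mention dilution: "Biomarker values above the Upper Limit of Quantification (ULOQ) will be imputed as ULOQ and values below the LLOQ will be imputed as LLOQ/2".

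SAP 2.7.3 treats laboratory results differently. A result given as <x is taken as half of x and a result given as >y is taken as y, so the substitute comes from the bound reported for that sample.

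**The concern.** Within a few lines the SAP writes the limit, and the limit times the dilution factor, as two different quantities, and then imputes from the first. A programmer who follows the text will drop the factor.

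Above range, the imputed number then contradicts the datum. A sample known to exceed ULOQ × DF is analysed as if it equalled ULOQ. Another diluted sample, read within range and reported somewhere between ULOQ and ULOQ × DF, is analysed at its measured value. The larger sample then ranks below the smaller one.

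At stake are the summaries, mixed models and plots of the exploratory biomarkers. The groups are small, so a single affected value can move a group mean noticeably. The listing would show the reported bound while the table and model use a number DF-fold lower.

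**Working it through.** The plan gives no figure to reproduce here, so the check applies the rule as written.

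**Inputs from the documents.** Reporting form, imputation rule and log scale: SAP 2.11. MAS825 sequence: 28 × 4/14 = 8 participants (SAP Section 3). DFV890 sessions by dose, from the sequences in SAP 2.1.1.2 with 8, 8 and 2 participants in sequences 2, 3 and 4: 10 mg 8 + 2 = 10; 25 mg 8 + 8 + 2 = 18; 50 mg 8 + 2 = 10; 100 mg 8 + 8 + 2 = 18.

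**Assumed, because the documents do not give them.** Working range 1 to 100 in arbitrary units; DF of 2, 4 or 10.

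**Step 1: one value.** Above range, the reported bound is > ULOQ × DF and the SAP enters ULOQ. The ratio to the bound is 1/DF and the log-scale error is −ln(DF). Since the true value exceeds the bound, this is the smallest the error can be. Below range, the reported bound is < LLOQ × DF; the SAP enters LLOQ/2, whereas half the reported bound is LLOQ × DF/2.

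| DF | Reported high | SAP enters | Log error | Reported low | SAP enters | Half the bound |
|---|---|---|---|---|---|---|
| 1 | >100 | 100 | 0 | <1 | 0.5 | 0.5 |
| 2 | >200 | 100 | −0.69 | <2 | 0.5 | 1 |
| 4 | >400 | 100 | −1.39 | <4 | 0.5 | 2 |
| 10 | >1000 | 100 | −2.30 | <10 | 0.5 | 5 |

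Without dilution (DF 1) the two rules agree.

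**Step 2: ranking.** At DF 10, a sample reported as >1000 is entered as 100. A second sample, also diluted tenfold and read at 30, is reported and analysed as 300. The larger one is analysed at a third of the smaller.

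**Step 3: group geometric mean.** With one affected above-range value among n, and compared with entering the reported bound, the factor is exp(−ln(DF)/n). This is unadjusted arithmetic, not a model fit.

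- MAS825, n = 8, DF 2: 0.693/8 = 0.087, factor 0.92 (−8%).
- MAS825, n = 8, DF 4: 1.386/8 = 0.173, factor 0.84 (−16%).
- MAS825, n = 8, DF 10: 2.303/8 = 0.288, factor 0.75 (−25%).
- DFV890 100 mg, n = 18: 0.693/18 = 0.0385 (−3.8%) at DF 2; 2.303/18 = 0.128 (−12%) at DF 10.

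**Step 4: the SAP's own warning.** The bias footnote in SAP 2.11 appears only when more than 20% of values in a group at a time point are imputed. One in 8 is 12.5%, so a 25% shift would carry no footnote.

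**The case against.** The best defence is that LLOQ/2 and ULOQ in the imputation lines are shorthand for the limits just reported, factor included. SAP 2.7.3 works that way for laboratory data, and SAP Section 1 places derivation details in a programming specification that is not part of these documents. The authors may have meant this. Nothing in SAP 2.11 says so, however, and it writes the limit with and without the factor as distinct quantities. If the shorthand was intended, one line settles it.

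A second defence is that the problem would be visible. Tables give the frequency of out-of-range values, plots mark imputed points, listings show the reported bound, and no summary is produced if more than half of a biomarker's data are imputed. That stands, but these measures do not correct the number entered.

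Three stronger readings are tempting and are not supported.

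- *The primary analysis is biased.* The rule sits in the exploratory biomarker section, and Protocol 9.5.1 confines its version to those analyses. SAP 2.5.6 anticipates baseline values below quantification for the primary outcome and plans an analysis without those participants, but it says nothing about dilution. The shifts above should not be set against the planned DFV890 effect on IL-6 and IL-18.
- *The low-end rule creates spurious reductions.* LLOQ/2 lies between 0 and LLOQ × DF, so it contradicts no observation. A false reduction would need dilution to differ between baseline and later samples, and no such pattern is documented.
- *The MAS825 target-capture markers will be hit hardest because they accumulate and need dilution.* The documents list these markers but say nothing about accumulation, dilution or above-range results.

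**Conclusion.** The rule as written gives a wrong value for one definite kind of sample: diluted and still above range. It is entered DF-fold too low relative to its own reported bound, and it can fall below smaller measured samples if another diluted sample was quantified between ULOQ and ULOQ × DF. One such value would lower the MAS825 geometric mean by about 8% (DF 2) to 25% (DF 10), and less in a group with more observations. Below range, the fault is only inconsistency with the half-bound convention used in SAP 2.7.3.

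This rests on a literal reading of SAP 2.11 and on assumed dilution factors. How often such samples occur is not stated, and if there are none the error is zero. The finding is limited to the exploratory biomarkers. It is worth correcting because the rule is wrong on its face and the correction is nearly free, not because a large bias has been shown.

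**What to change.** Replace the two imputation lines in SAP 2.11 so that each substitute is taken from the bound reported for that sample: ULOQ × dilution factor above range, and (LLOQ × dilution factor)/2 below range. This matches SAP 2.7.3. Record it in SAP Section 4 as a clarification of Protocol 9.5.1, which does not mention dilution.

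The cost is two lines of text and one programming change. By the SAP's own description, the reported result already carries the factor. There is one small downside: a diluted below-range sample may be imputed above a low value measured in an undiluted sample. With the assumed range and DF 10, <10 becomes 5, above an undiluted sample read at 2, although the true concentration could be lower than 2. That is a limit of any single-value substitution and does not outweigh the correction above range.
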